8.2 Data Collection and Management

Investigator responsibilities are set out in the ICH guideline for Good Clinical Practice (GCP) and in the US Code of Federal Regulations.

Investigators must enter study data onto CRFs or other data collection system. The Investigator will permit study-related audits by Novartis or its representatives, IRB/EC review, and regulatory inspection(s) (e.g., FDA, EMEA, TPP), providing direct access to the facilities where the study took place, to source documents, to CRFs, and to all other study documents.

The Investigator, or a designated member of the Investigator's staff, must be available at some time during audits to review data and resolve any queries and to allow direct access to the subject's records (e.g., medical records, office charts, hospital charts, and study related charts) for source data verification. The data collection must be completed prior to each visit and be made available to the Novartis representative so that the accuracy and completeness may be checked.

8.3 Overall Study Monitoring for Collaborating Sites

The coordinating center for this multicenter study is the Clinical Trials Office of the Winship Cancer Institute of Emory University. Monitoring plan for this study will therefore follow the established Data Safety and Monitoring Plan for all investigator-initiated phase II trials at the Winship. The Emory University WINSHIP CANCER INSTITUTE monitoring team will have primary responsibility to coordinate, conduct and/or oversee all study auditing. The study will be audited at least annually in addition to the reporting requirement established by the IRB. If the Monitoring Committee determined that an external audit should be conducted, the committee shall be responsible for appointing the external auditors. The scope and conduct of the audit will be established by the committee and support for the audit will be provided by the Emory WINSHIP CANCER INSTITUTE Monitoring Office.

Monitoring Committee: The committee members shall consist of faculty members, a research nurse, the Clinical Trials Director and/or Associate Director, the Medical Director of Clinical Trials, the Director of the Phase I program and the Regulatory and Compliance Manager. The Monitoring Committee reviews all auditing, DSMB composition and reports, and recommends corrective action if needed to the PI.

The committee will:

Review all SAEs from all sites at the time of report to the WINSHIP CANCER INSTITUTE

Review risk/benefit ratio and report to Emory IRB at the time of continuing review

Review the protocol, amendments, informed consent documents and IRB submissions

Meet with the PI for clarification of objectives and collection tools for these objectives.

The Monitoring Office: This office consists of auditors and support staff and is administered by the Regulatory and Compliance Manager. The Clinical Trials Medical Director is available for ongoing consultation. Auditing will be performed by a qualified auditor who has access to the Medical Director of Clinical Trials, or a designee if he is involved in the study, for guidance and resolution of medical questions. The Emory WINSHIP CANCER INSTITUTE Monitoring Office will audit data integrity and safety information for all participating sites according to the approved schedule in the Winship DSMC Standard Operating Procedures and Policies.

The following will be inspected during the monitoring visit

- i. Review of data integrity
- ii. Documentation of the qualifications, training and experience of the PI and other study staff
- iii. Eligibility of consented/enrolled patients
- iv. Informed consent document and process
- v. Verification that the local PI and staff are performing trial functions in accordance with protocol
- vi. Accuracy, completeness and timeliness of data
- vii. Accuracy and completeness of all source documentation
- viii. Response evaluation: verify that responses are identified according to the protocol definition of response for any response that is a major endpoint
- ix. Toxicity
- x. Appropriate reporting of all AEs and SAEs as required by GCP, the protocol, IRB regulations, sponsor's SOPs and other regulatory requirements

The monitor shall meet with RN/Coordinator assigned to the trial to:

provide an itemized review of the deficiencies to the RN/Coordinator and remove items from itemized review which are corrected during this meeting

review and document corrections; the RN/coordinator should indicate any remaining deficiencies and provide corrective action plan for resolution

prepare summary report for PI and Monitoring Committee to include summary of systematic deficiencies, significant protocol deviations, summary of remaining deficiencies and RN/coordinator corrective action plan, recommendations for data collection, protocol revision for clarity

The Monitor shall meet with the overall PI to discuss the report and document the PI's responses prior to submitting final report to the Monitoring Committee

The final Monitoring Committee review of audit report and PI response and PI summary of protocol to date will be included in the annual renewal submission.

Egregious data insufficiencies that may impact the scientific integrity of the trial are reported to the Medical Director and Clinical Trial Review Committee.

Please see the attached supplementary Emory University WINSHIP CANCER INSTITUTE data safety monitoring plan policy document for a complete detail of the monitoring plan.

9 Statistical methods and data analysis

All treated subjects will be included in the analysis of efficacy and safety.

Demographic and baseline characteristics will be summarized using descriptive statistics. The toxicities will be tabulated by organ system. Time to disease progression and overall survival will be evaluated using the Kaplan-Meier method.

Correlative analysis will be exploratory in the context of this Phase II screening trial.

Post treatment correlatives will be collected on a limited number of patients who progress on the single agent arm. These will allow us to explore whether biological mechanisms postulated to be specific to the investigational agents is involved, and if dynamic changes in putative targets distinguish between responders and non-responders in this limited subset of patients.

Analysis of baseline measurements obtained on all patients: Three types of analysis are planned: (a) Conditional analysis: does the correlate have an impact on response rate if the patient is treated with the specific investigational agent? (b) Marginal analysis: does the correlate have an impact when combining the two agents? and (c) Interaction: does the correlate have an impact differing by the treatment arm?

Due to the variability in the baseline expression of correlative endpoints such as somatostatin receptor and mTOR protein, the limited sample-size and response rate, and pre-determined sample-size, no formal power calculation is presented for this exploratory research.

9.1 Objective RR and PFS as endpoints

Within Arm: Using a Simon's 2-stage MinMax design, 18 patients will be enrolled into stage I. At least one objective response is required to proceed to stage II accrual of 10 additional patients for a total of 28 patients per arm. If 3 or more patients achieve objective response following total

accrual, the particular treatment arm will be deemed worthy of further clinical evaluation in this disease. For response determination, any patient who progress prior to satisfying the objective response criteria will not be replaced but will be deemed evaluable for response evaluation and classified as a non-responder.

Between Arms: Any treatment arm closed to accrual after the first stage interim analysis will be considered an inferior arm and will be excluded from comparison for the winner of trials. The arm with the best overall RR at the end of full enrolment will be adjudged the winner to be considered for further development provided there are at least 3 objective responses. Only in the event of identical RR between 2 or more arms or if none of the arms met the RR criterion (less than 3 objective responses after full patient enrolment) would the 1-yr PFS rate be employed to determine a winner. Based on recent clinical trials of targeted agents in similar patient population, 90% of patients were alive at 1 year and median progression free survival ranged between 9 and 18 months.⁸⁻¹⁰ We assume a conservative estimate that only 20% of the patients will be progression free at 1 year if the treatment is ineffective while 50% or more of the patients will be progression free at the same time point with an effective regimen. For this purpose, a 1-year PFS rate of 50% or greater will be considered sufficient activity to justify further evaluation of the treatment in this disease. Assuming a 20% or lower 1-year PFS rate with an inactive regimen and a 50% or greater rate with an active regimen, 28 patients enrolled onto each arm will classify the treatment as having sufficient activity for further evaluation with a probability of 0.95 (power against the alternative hypothesis $p = 0.05$). In this respect, the arm with the highest 1-yr PFS rate will be judged the winner. In the event of a tie between the arms for both the RR and 1-yr PFS rate, the arm with the best profile in terms of safety and tolerability will be considered the overall winner to be selected for further evaluation in this disease. The power calculation for PFS assessment assumes full enrolment of 28 patients to the treatment arm, therefore any arm closed to further accrual following the initial interim analysis will not be eligible for the PFS endpoint assessment. The investigational agents in this trial have not been previously studied in thyroid cancer; therefore we are unable to accurately determine the drop-off rate. Nonetheless, all patients

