The study design for this Phase II trial is a randomized screening design with multiple arms. A simple winner arm is selected only from the arms shown to be superior to the historical control. Between arms: Eligible patients will be randomly assigned to one of three arms to receive single agent pasireotide, everolimus or the combination of both drugs. Randomization is conducted with a block of 3 patients in order to balance the enrollment in each arm (The first of the 3 patients entered consecutively is randomly assigned to any of the 3 arms; the second patient is randomly assigned to one of the remaining 2 arms and the third patient to the last arm).

Within arms: Within each of the 3 arms, a Simon's 2-stage MinMax design is used. Eighteen evaluable patients will be enrolled into stage I. At least one objective response is required to proceed to stage II accrual of 10 additional patients for a total of 28 patients per arm. At least 3 patients must achieve objective response for the particular treatment arm to be considered worthy of further clinical evaluation in this disease.

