Between Arms: Any treatment arm closed to accrual after the first stage interim analysis will be considered an inferior arm and will be excluded from comparison for the winner of trials. The arm with the best overall RR at the end of full enrolment will be adjudged the winner to be considered for further development. In the event of identical RR between the arms or if none of the arms met the RR criterion (less than 3 objective responses after full patient enrolment), the 1-yr PFS rate will be employed to determine a winner. Based on recent clinical trials of targeted agents in similar patient population, 90% of patients were alive at 1 year and median progression free survival ranged between 9 and 18 months.⁸⁻¹⁰ We assume a conservative estimate that only 20% of the patients will be progression free at 1 year if the treatment is ineffective while 50% or more of the patients will be progression free at the same time point with an effective regimen. For this purpose, a 1-year PFS rate of 50% or greater will be considered sufficient activity to justify further evaluation of the treatment in this disease. Assuming a 20% or lower 1-year PFS rate with an inactive regimen and a 50% or greater rate with an active regimen, 28 patients enrolled onto each arm will classify the treatment as having sufficient activity for further evaluation with a probability of 0.95 (power against the alternative hypothesis $p = 0.05$). In this respect, the arm with the highest 1-yr PFS rate will be judged the winner. In the event of a tie between the arms for both the RR and 1-yr PFS rate, the arm with the best profile in terms of safety and tolerability will be considered the overall winner to be selected for further evaluation in this disease. The power calculation for PFS assessment assumes full enrolment of 28 patients

to the treatment arm, therefore any arm closed to further accrual following the initial interim analysis will not be considered for PFS endpoint assessment.

Figure 4-1: Statistical Consideration for Power and Sample Size

Primary Efficacy Decision Using Simon's MinMax Design Based on RR: P0 = 5% vs. P1 = 15% Power = 80%; α = 0.20	
First Stage Sample Size	18
Upper Limit for First Stage Rejection of Drug	0
Maximum Sample Size	28
Upper Limit for Second Stage Rejection of Drug	2

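### The 1-year PFS fallback gives the win to the highest-ranked arm without applying the 50% bar or allowing for no winner, and the 50% bar does not match the stated 0.95 power

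*Combined protocol and SAP*

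**What the plan says.** Section 4 sets a general condition: "A simple winner arm is selected only from the arms shown to be superior to the historical control". It also ties merit to response: "At least 3 patients must achieve objective response for the particular treatment arm to be considered worthy of further clinical evaluation in this disease". Section 9.1 repeats the 3-response rule for each arm. It names the arm with the best RR as winner only if that arm has at least 3 responses.

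Both sections then give 1-year PFS a role when arms tie on RR, or "if none of the arms met the RR criterion (less than 3 objective responses after full patient enrolment". Arms closed after stage I are excluded from that comparison. The same paragraph contains three further statements, in this order:

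- A 1-year PFS rate of 50% or more counts as enough activity to justify further evaluation.
- With 20% for an inactive regimen and 50% for an active one, 28 patients per arm give a probability of 0.95 of classifying the treatment as active. The table in Figure 4-1 adds a two-sided α of 0.05.
- "In this respect, the arm with the highest 1-yr PFS rate will be judged the winner".

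If RR and PFS both tie, safety and tolerability decide.

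**The concern.** In section 9.1 the RR winner sentence carries its own condition, at least 3 responses. The PFS winner sentence carries none and only ranks. Neither section says what happens if no fully enrolled arm shows adequate PFS. A team following the ranking sentence would name a winner whenever at least one arm gets past stage I, which takes a single response among 18 patients.

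The 50% statement does not settle the matter, because it supports two different rules. Read as an observed rate, it means at least 14 of 28. Read through the power statement, it means a test that rejects 20% with about 95% power at 50%, and that cut is much lower. An arm with 10 to 13 of 28 progression-free (36% to 46%) is active on the power statement, inactive on the 50% statement, and the winner on the ranking sentence if it comes first. Section 4's limit to arms that beat the historical control does not help here, since the plan does not say how that is shown on PFS.

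At stake is which arm, if any, is put forward for further development.

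**Working it through.** **Inputs.** Figure 4-1 gives "P0 = 5% vs. P1 = 15% Power = 80%; α = 0.20", with 18 patients in stage I and 28 in total. Section 9.1 gives the continuation rule ("At least one objective response is required to proceed to stage II accrual of 10 additional patients") and the final rule ("If 3 or more patients achieve objective response following total"). There are three equally allocated arms. The 1-year PFS rates are 20% (inactive) and 50% (active), with 28 patients per arm.

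**The plan's RR design reproduces.** An exact search for the minimax two-stage design returns 18/28, stopping at 0 responses in stage I and rejecting at 2 or fewer overall. The attained error is 0.158 (limit 0.20) and the power is 0.803.

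**One arm at RR 5%:**

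- Stops at stage I: 0.95^18 = 0.397.
- Reaches at least 3 responses: P(1 of 18) × P(≥2 of 10) + P(2 of 18) × P(≥1 of 10) + P(≥3 of 18) = 0.3763 × 0.0861 + 0.1683 × 0.4013 + 0.0581 = 0.158.
- Completes with fewer than 3 responses: 1 − 0.397 − 0.158 = 0.445.

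**Three independent arms at RR 5%:**

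- At least one arm passes on RR: 1 − (1 − 0.158)^3 = 0.403.
- No arm passes but at least one completes, so the fallback decides: 0.842^3 − 0.397^3 = 0.534.
- Winner named under ranking alone: 0.403 + 0.534 = 0.937, which equals 1 − 0.397^3.

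**PFS cuts on 28 patients (exact binomial):**

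| Cut | Observed rate | One-sided error at 20% | Power at 50% |
|---|---|---|---|
| ≥10 | 36% | 0.039 | 0.956 |
| ≥11 | 39% | 0.015 | 0.908 |
| ≥14 | 50% | 0.0004 | 0.575 |

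A two-sided 0.05 normal approximation gives power 0.946, close to the stated 0.95. In exact terms, 0.95 needs the cut at 10, whose upper-tail error exceeds 0.025. The first cut with error below 0.025 is 11, with power 0.908. No reading that requires an observed 50% comes near 0.95.

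**Winner probability with a bar in the no-arm-passed fallback.** With q the chance that an inactive arm clears the bar, and PFS independent of response, the fallback adds 0.842^3 − (0.842 − 0.445q)^3.

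- ≥10/28, q = 0.0391: adds 0.036, total 0.439.
- ≥14/28, q = 0.0004: adds 0.0004, total 0.404.

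A simulation of 1,000,000 trials agrees: 0.937, 0.439 and 0.403.

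**Sensitivity to the inactive RR:**

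| Inactive RR | Winner, ranking alone | At least one arm passes on RR |
|---|---|---|
| 5% | 0.937 | 0.403 |
| 3% | 0.807 | 0.140 |
| 2% | 0.664 | 0.051 |
| 1% | 0.419 | 0.008 |

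**The case against.** The strongest reply is that the paragraph should be read as a whole: clear the 50% bar, then rank the arms that cleared it. The 50% statement is introduced for this very decision, and section 4 restricts winners to arms that beat the historical control. On that reading, with 14 of 28 as the bar, the fallback adds about 0.0004 to the chance of a false winner. This largely stands. A reader might infer from the ranking sentence that the plan states no bar and that 94% is its false-winner rate. The documents do not support that: a bar is stated, and 94% describes one sentence followed alone.

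A second reply is that letting an arm through on PFS after it missed on RR is deliberate. This also stands. PFS is a primary endpoint (sections 3.1 and 7.4), and Figure 4-1 tabulates a separate efficacy decision on it. Section 1.1 describes disease stabilization as the usual outcome with targeted agents, so an arm could beat the historical control on PFS with few responses. The second route does not itself contradict section 4.

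Third, a reader might infer that the fallback turns a negative trial into a positive one. That goes too far. The trial is described as non-comparative, its objectives include each arm's RR and PFS, and the winner is only a candidate for further development.

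None of this resolves the missing no-winner outcome or the mismatch between 50% and 0.95.

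**Conclusion.** The point holds as a defect of specification. The sentence that awards the win under the fallback neither applies the stated bar nor allows for no winner, and the bar, read as an observed rate, has power 0.575 where the plan states 0.95. Depending on the reading, the chance of naming a winner among three inactive arms is 94% (ranking alone), 44% (at least 10/28) or 40% (at least 14/28). About 40 points of each figure come from applying the RR rule to three arms, and a PFS bar in the fallback does not change that part. The fallback is not a rare corner: with inactive arms at RR 5%, it decides more often (0.534) than an RR pass (0.403).

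These figures assume independent arms, an inactive RR of exactly 5% (the ranking-only figure falls below that), 1-year PFS of 20% independent of response, and a known 1-year status for all 28 patients. The last assumption is generous, since Figure 4-1 plans no follow-up after the 30-month enrolment.

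**What to change.** In sections 4 and 9.1, state that when no arm has 3 responses, the fallback winner must be a fully enrolled arm that meets one defined PFS criterion, and that if no arm meets it, no winner is named. Choose one criterion:

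- at least 10 of 28 progression-free at 1 year, which rejects 20% at one-sided 0.039 and keeps the stated 0.95 power; the 50% statement and the two-sided α in Figure 4-1 then need rewording to agree; or
- at least 14 of 28, which keeps the 50% bar; the power must then be restated as about 0.57.

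Align section 4's sentence on superiority to the historical control, so that it says superiority may be shown on RR or on this PFS criterion. Ties on RR among arms that already have 3 or more responses can still be broken by PFS ranking, because those arms have met the activity rule.

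The change is one sentence in each section plus consistent figures. It needs no more patients. The downside is that some trials will end without a winner.

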Secondary Efficacy Decision Based on 1-Year PFS Rate Endpoint at the End of Complete Enrolment; Total enrolment of 28 patients per arm Duration of enrolment: 30 months Additional follow-up time: None 1-year PFS Rate	
P0	20%
P1	50%
Power	95%
2-sided α	0.05

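### The only stated 1-year PFS activity mark (50%) is the design alternative itself; used as an observed cut-off it has about 57% power, not 95%, and no other PFS cut-off is given

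*Combined protocol and SAP*

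**What the plan says.** The between-arms text appears in both Section 4 and Section 9.1. It takes 20% as the 1-year PFS rate of an ineffective treatment and assumes that "50% or more of the patients will be progression free at the same time point with an effective regimen". It then says that "a 1-year PFS rate of 50% or greater will be considered sufficient activity to justify further evaluation of the treatment". The following sentence claims that "28 patients enrolled onto each arm will classify the treatment as having sufficient activity for further evaluation with a probability of 0.95".

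Figure 4-1 in Section 4 treats the two endpoints differently. For response it prints rejection limits for each stage: 0 of 18, and 2 of 28 under "Upper Limit for Second Stage Rejection of Drug". The block headed "Secondary Efficacy Decision Based on 1-Year PFS Rate Endpoint at the End of Complete Enrolment" gives only P0 = 20%, P1 = 50%, power 95% and two-sided alpha 0.05. It has no count, critical rate or confidence-limit rule.

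The remaining PFS decision text is a ranking: "the arm with the highest 1-yr PFS rate will be judged the winner". The nearest statement of an estimator is in the opening of Section 9: "Time to disease progression and overall survival will be evaluated using the Kaplan-Meier method". It is not tied to a PFS decision. Section 7.4 names PFS as a primary endpoint alongside response rate.

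**The concern.** The 50% figure does two jobs in adjacent sentences. First it is the alternative hypothesis, then it is the level that counts as sufficient activity. The power sentence reuses the idea of sufficient activity, so a reader will take 0.95 as the power of the 50% rule. A pass mark set at the alternative has power near one half by construction, because the estimate falls below its own true value about half the time.

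If 50% was never meant as a pass mark, PFS has no activity cut-off at all. Either way, an arm with 11, 12 or 13 of 28 progression-free at 1 year could be called active or inactive after the data are seen. This matters most if no arm reaches 3 responses, when PFS alone could carry a regimen forward. Section 4 also restricts the winner to arms shown to beat the historical control, and without a PFS cut-off that restriction cannot be applied in the fallback.

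**Working it through.** **Inputs** (Section 9.1 and Figure 4-1): n = 28 per arm, P0 = 0.20, P1 = 0.50, two-sided alpha 0.05, stated power 0.95. Assumption for the exact figures: 1-year status is known for all 28, so a Kaplan-Meier estimate equals the observed proportion. X is the number progression-free at 1 year.

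**Step 1. Reproduce the 95%.** One-sample test against P0, normal approximation with null variance:
- Cut-off = 0.2 + 1.96 × √(0.2 × 0.8 / 28) = 0.2 + 1.96 × 0.0756 = 0.348.
- Power = Φ((0.5 − 0.348) / √(0.5 × 0.5 / 28)) = Φ(0.152 / 0.0945) = 0.946.

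The stated 95% is therefore right for a test against 20%, whose cut-off is 34.8%.

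**Step 2. Candidate cut-offs, exact binomial, n = 28.**

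| Pass if | Observed rate | P(pass) at true 20% (one-sided alpha) | P(pass) at true 50% (power) |
|---|---|---|---|
| X ≥ 10 | 35.7% | 0.039 | 95.6% |
| X ≥ 11 | 39.3% | 0.015 | 90.8% |
| X ≥ 14 | 50.0% | 0.0004 | 57.5% |

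The exact two-sided p-value against 20% is 0.0545 at 10/28 and 0.0168 at 11/28. At the stated two-sided 0.05 the exact cut-off is therefore 11/28; 10/28 just misses. The exact 95% lower limits agree: 18.6% at 10/28 and 21.5% at 11/28.

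**Step 3. Can a larger sample rescue a 50% pass mark?** P(X ≥ n/2) at a true 50% is 57.5% for n = 28, 54.0% for n = 100 and 51.3% for n = 1000. It cannot. At n = 28 the true rate must be 63.4% before X ≥ 14 has 95% probability.

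**Step 4. How often do the two readings disagree?** Against the exact two-sided test they differ at 11 to 13 of 28 (39–46%).
- At a true 50%: 0.9075 − 0.5747 = 0.333.
- The plan cites trials in which "median progression free survival ranged between 9 and 18 months". Assuming exponential PFS, the 1-year rates are 0.5^(12/9) = 39.7% and 0.5^(12/18) = 63.0%. The probability of 11–13 is 41% at the low end and 5% at the high end.

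Against the normal-approximation test of Step 1, 10/28 also passes (z = (0.357 − 0.2)/0.0756 = 2.08). The zone widens to 10–13, with probability 0.9564 − 0.5747 = 38% at a true 50%, and 55% and 5% at the two ends of the range.

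**Step 5. Incomplete follow-up.** Figure 4-1 gives 30 months of enrolment and no additional follow-up. With uniform accrual (assumption), 28 × 18/30 ≈ 17 patients have 12 months of potential follow-up, so a Kaplan-Meier estimate would be needed. By normal approximation its chance of reaching 50% at a true 50% is still about one half.

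**The case against.** The strongest reply is that 50% was only ever the alternative. The sentences on either side use it as an assumed rate, Figure 4-1 lists it as P1, Section 4 speaks of superiority to a historical control, and the stated inputs reproduce 94.6%. On that reading the 95% is not an arithmetic error, and the 57% answers a rule the authors did not intend. This stands as far as it goes. It leaves the PFS decision with no pass mark, and the only activity criterion in print is still the 50% sentence.

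A second reply is that the consequence is small. PFS decides only when response rates tie or no arm has 3 responses, the operative rule is a ranking, and an arm with at least 3 responses in 28 is worthy of further evaluation whatever its PFS. That is correct and limits the weight of the point. It does not remove it, because PFS is a named primary endpoint and the activity sentence applies to each arm.

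A third reply is that the three-digit figures assume complete 1-year status, which the printed follow-up does not guarantee. That also stands; the conclusion of roughly one half does not depend on it.

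**Conclusion.** The concern holds. The printed activity mark and the printed power do not belong to the same rule. As an observed pass mark, 50% gives 57.5% power at a true 50%, so an effective arm would be judged inactive about 43% of the time. As a target true rate it is compatible with the 95%, but the cut-off that delivers that power, near 35–39%, is not stated. The exact figures assume 28 patients with known 1-year status, and the probabilities over the 9–18 month range also assume exponential PFS. The effect is limited to the PFS activity judgement and to the tie-break and fallback selection. It should be corrected, but it does not undermine the response-rate design.

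**What to change.** In Figure 4-1 and in the between-arms text of Sections 4 and 9.1, label 50% as the target true 1-year PFS rate (P1). Then state one cut-off, its estimator and its own operating characteristics. Options:

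- **Count rule.** An arm shows sufficient activity if at least 11 of 28 patients are progression-free at 1 year (exact one-sided alpha 0.015 at 20%, power 91% at 50%). At least 10 of 28 keeps power at 95.6%, but its exact two-sided p of 0.0545 means the stated alpha must be reworded.
- **Confidence-limit rule.** The 95% lower limit of the Kaplan-Meier 1-year PFS estimate exceeds 20%. The interval method must be named because it can change the verdict: at 10/28 the exact limit is 18.6% and fails, while the Wilson limit is 20.7% and passes. The sponsor should calculate power for the follow-up actually planned.
- **Keep 50% as the observed pass mark** and restate the power as about 57%.

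In each case, restrict the highest-PFS ranking to arms that clear the cut-off, so that it agrees with the historical-control restriction in Section 4.

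The cost is wording in three places and no extra patients. The 11-of-28 rule lowers the quoted power from 95% to 91%. A count rule needs 1-year status for everyone, so the PFS read-out may come up to 12 months after enrolment ends; otherwise the power is lower than quoted.
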